Recruitment of infants and young boys: We will enroll children from age 1 month through age 30 months. Follow-up examinations will be performed 6-month and 12 months after the baseline visit. The specific goal would be to determine whether the average change in Bayley-III scores differ from the scores of the boys who are untreated. A total of 25 children will be needed and we expect to follow them every 6 months for one year. Based on the recruitment in the study of untreated infants we expect to recruit these children over 15-24 months. We are allowing for a potential drop out of 5 infants.

Statistical considerations and Power Calculations for current study.

Follow-up of twenty untreated infants and young boys with DMD showed that the average negative change in the Bayley III gross motor scaled score over six months was -0.4. If the effect size of therapy is an increase of 1.5 points on this scaled score, then 19 infants would be required for 95% confidence to detect a difference. If the effect size of corticosteroids is +2.0 points only 11 infants would be required. We have chosen to enroll 24 infants, with the expectation that 4 might be lost to follow up or drop out of the study. While we have calculated the effect size for six months, additional data in a small subset suggest there is further decline over 12 month (total average decline of 1.0 point in 12 boys. The six month and 12 month follow-up of the cohort will be analyzed and reported to the MDA.

Study Procedures and Visits

The fundamental goal of this work is to determine if two reliable developmental assessments (Bayley-III and NSAA) in young boys with DMD will detect a change in gross motor function in infants and young boys treated with twice weekly oral prednisone. We will follow children for one year and they will be ages 1 month through 30 months at enrollment.

There will be a total of six visits, Baseline, and at 1, 3, 6, 9, and 12 months.

Baseline evaluation and visits at 6 and 12 months will include:

a) History to include age of walking defined as 10 independent steps

b) Every 6 months Vital signs including height, weight, heart rate, blood pressure

Height will be assessed in two ways

1. Measurement of supine length if child is not able to stand

2. Standing height if child is able to stand

c) Every 6 months the following will be performed

1. Bayley-III Scales of Infant Development.

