This test consists of a standardized assessment of cognitive, language, and motor using small toys, blocks and books. For infants there is a special set of activities to assess the muscle function called Bayley-III infant motor scale which has both a fine motor and gross motor component. This assesses the degree of body control, large muscle coordination, finer skills of the hands and fingers, dynamic movements. This will be done through observations and questions. The Bayley-III infant mental scales will test language and cognition.

2. North Star Ambulatory assessment North Star Ambulatory Assessment

(NSAA). The NSAA^{40, 41} assesses functional activities including standing, getting up from the floor, negotiating steps, hopping, and running. The assessment is based on a 3 point rating scale of 2= ability to perform the test normally, 1= Modified method or assistance to perform test, 0=unable to perform the test. Thus, total score can range from 0 (completely non-ambulant) to 34 (no impairment on these assessments).

3. Ultrasound of the muscle (this measure will be followed only on infants recruited from the Washington University Site)

This will be done by keeping the ultrasound probe on biceps and quadriceps to see the image of the muscle for structural changes. As the muscle changes the ultrasound will reflect the changes.

4. EIM of Muscle. This will be performed at all sites

5. Behavior: The Adaptive Behavior Assessment Scale (ABAS) is a well-validated measure of adaptive behavior and will be tested every 6 months.

6. Caregiver Burden: This will be tested by filling out the Caregiver stress questionnaire.

7. Complete Physical Examination and Neurological examination

The Visits at 1, 3, and 9 months will be safety visits which can be performed locally or on site. If laboratory studies are performed locally, phone visit will occur.

Table 1. Schedule of Events

Study Period (+7 days)	Month 0	Month 1*	Month 3*	Month 6	Month 9*	Month 12
Informed consent	X					
Vital signs, Height, Weight, Occipital Frontal Circumference BMI (kg/m ²)	X			X		X
Medical History	X	X	X	X	X	X
Medication review	X	X	X	X	X	X
Con Medication review	X	X	X	X	X	X
Medical Events		X	X	X	X	X
Adverse Events		X	X	X	X	X
Physical examination	X			X		X
Neurological Examination	X			X		X
Electronic Impedance Myography	X			X		X
Ultrasound for WU infants only	X			X		X
North Star Ambulatory Assessment	X			X		X
Bayley-III Scales of Infant development	X			X		X

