Adaptive Behavior Assessment Scale	X			X		X
Care giver Burden assessment	X					X
CBC/Diff	X	X	X	X	X	X
CPK	X	X	X	X	X	X
Sodium	X	X	X	X	X	X
Potassium	X	X	X	X	X	X
Chloride	X	X	X	X	X	X
CO ₂	X	X	X	X	X	X
BUN	X	X	X	X	X	X
Fasting Serum Glucose	X	X	X	X	X	X

**Phone call or on site assessments will take place at visits 1, 3, and 9 months.

Criteria for dose reduction:

Prednisone dose will be reduced for

- 1) An increase in Body mass index (BMI) (kg/m²) greater than 10% over 6 months
- 2) A fasting blood sugar greater than 100mg/dl after dietary modification
- 3) An increase in diastolic blood pressure greater than 10mm Hg over upper limit of normal for age
- 4) An increase in systolic blood pressure greater than 15mm Hg since the last visit
- 5) Otherwise, non-manageable side effects including irritability or difficulty sleeping.

Data Management Repository

The informatics component of the proposed specific aims will provide a centralized data management repository. The system will provide a secure web-based application designed to harmonize data from the all-participating institutions. The functionality of the system will include data entry, data integration, data validation and quality control, searching, reporting, and exporting. The system will have three core components to include administration, institution, and investigator data requests. The administration component will allow a defined member of the MDA DMD CRC Network access to data generated from their sites and data from the network at large, upon validation that data request forms are from participating institutions. The approval process will be defined in the Manual of Operations. Once approved, the data set is generated and released to that approved investigator. **The data that will be submitted to the central data management repository will include the following information.**

1) Demographics

- ID#
- Date of Birth
- Date of study visit
- DMD Gene Mutation
- Age (derived from DOB, Date of study)
- Height/Length in centimeters
- Weight in kilograms
- Body Mass Index
- Occipital Frontal Circumference in centimeters

2) Assessments

- a) Bayley-III scales of Infant Development
 - b) North Star Ambulatory Assessment
 - c) Adaptive Behavior Assessment Scale (ABAS)
 - d) Caregiver Burden
- 3) History including Dietary history recorded
 - 4) Medical events recorded
 - 5) Adverse events recorded
 - 6) Concomitant medications recorded

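### Blood pressure and weight are scheduled only at months 0, 6 and 12, so two dose-reduction rules have no on-treatment reading before month 6 and the per-kg dose has no scheduled weight at months 1, 3 or 9

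*Protocol*

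**What the plan says.** **Rules.** Criteria for dose reduction lists five triggers: a BMI rise over 6 months, raised fasting glucose after dietary change, "An increase in diastolic blood pressure greater than 10mm Hg over upper limit of normal for age", "An increase in systolic blood pressure greater than 15mm Hg since the last visit", and otherwise unmanageable side effects.

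**Schedule.** Study Procedures and Visits lists, for baseline and months 6 and 12, "Every 6 months Vital signs including height, weight, heart rate, blood pressure". The Table 1 row that begins "Vital signs, Height, Weight, Occipital Frontal Circumference BMI" is marked at months 0, 6 and 12 only. The recruitment paragraph agrees: "Follow-up examinations will be performed 6-month and 12 months after the baseline visit".

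**Other contacts.** "There will be a total of six visits, Baseline, and at 1, 3, 6, 9, and 12 months". Of three of these the protocol says "The Visits at 1, 3, and 9 months will be safety visits which can be performed locally or on site", and the Table 1 footnote adds "Phone call or on site assessments will take place at visits 1, 3, and 9 months". If the laboratory tests are local, the visit itself is by phone. Table 1 gives months 1, 3 and 9 history, medication review, medical and adverse events and blood tests including fasting glucose, but no vital signs and no physical examination.

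**Dose.** Objective 2 sets 5 mg/kg on two consecutive days, which is 10 mg/kg/week. Entry is from one month of age (Inclusion Criteria). The Introduction says that drug is supplied at every visit. Nothing says which weight sets the mg amount or when it is recalculated. The SAP is silent on dosing and safety.

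**The concern.** A dose-reduction rule protects a child only if the measurement behind it is taken. Aim 2d asks whether this regimen is tolerated and safe below 30 months of age, and the protocol creates safety visits at months 1 and 3 for early monitoring. If the schedule is followed exactly, a blood-pressure rise can go unmeasured for the first six months, and two of the five safeguards cannot act in that time. A rise in blood pressure need not produce a complaint, so questions about adverse events by phone do not replace a reading.

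The second issue is dose fidelity. Infants grow, the dose is per kg, and three of the five dispensing visits before month 12 (months 0, 1, 3, 6 and 9) have no scheduled weight.

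**Working it through.** **1. Rules against schedule (protocol only).**

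| Rule | Scheduled data | First on-treatment check |
|---|---|---|
| BMI over 6 months | 0, 6, 12 | Month 6, matching its own window |
| Fasting glucose | All six visits | Month 1 |
| Diastolic | 0, 6, 12 | Month 6 |
| Systolic | 0, 6, 12 | Month 6 |
| Side effects | History and events at 1, 3, 6, 9, 12 | Month 1 |

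Only the two blood-pressure rules lack data at the safety visits. The text and Table 1 agree, so this is not a damaged table.

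**2. Exposure before the first reading.** Two doses a week × 26.1 weeks = 52 doses by month 6. By month 1: 2 × 4.35 = 8.7, about 9.

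**3. Systolic comparator.** Taken literally, the visit before month 6 is month 3 and the visit before month 12 is month 9, and neither has a scheduled reading. Read as the last visit with vital signs, the comparisons are 6 v 0 and 12 v 6, and the rule works.

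**4. Dose drift, if the mg amount is fixed between weighings.** The dose is 10/(1+g) mg/kg/week for fractional gain g since the last weight. It falls below 9, 8 or 7 once g exceeds 0.111, 0.250 or 0.429. The protocol gives no growth data. For assumed linear six-month gains of 20%, 40% and 80%:
- average over the six months, 10·ln(1+g)/g: 9.1, 8.4, 7.3;
- just before month 6, 10/(1+g): 8.3, 7.1, 5.6;
- just before month 6 with weights and dose resets at months 1 and 3, 10(1+g/2)/(1+g): 9.2, 8.6, 7.8.

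**5. Chance systolic triggers.** Assume normal readings, no true change, and an SD of the difference between two readings of 8, 10 or 12 mm Hg. These SDs are not in the documents. One comparison exceeds 15 with probability P(Z > 15/SD) = 3.0%, 6.7%, 10.6%. Per child over the year, by simulation:
- two comparisons (6 v 0, 12 v 6): about 6%, 13%, 21%;
- five consecutive comparisons: about 15%, 31%, 46%.

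Now require a same-visit repeat that also exceeds 15. The two differences share the earlier reading, so they correlate 0.5 if the repeat is independent and 0.75 if it shares half the reading variance. The bivariate normal tail per comparison is 0.6%, 1.8%, 3.5% or 1.2%, 3.1%, 5.5%. Five times these gives ceilings of about 3%, 9%, 18% (independent) or 6%, 16%, 27% (half shared).

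**6. A true sustained rise of 20 mm Hg from month 1 (assumed).** One comparison flags it with probability P(Z > −5/SD) = 73%, 69%, 66%. Today that comparison comes at month 6, with nothing scheduled earlier. With readings at months 1 and 3 and no repeat, 75.5%, 73.8% and 73.4% are flagged by month 3. Requiring the repeat lowers the single-comparison figure to about 60%, 55%, 51% (independent) or 64%, 59%, 56% (half shared), by the same bivariate calculation. The added readings bring the earlier detection, and the repeat controls chance triggers at some cost in sensitivity.

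**The case against.** **Monitoring is not absent before month 6.** Adverse events, medication review and laboratory tests are scheduled at months 1, 3 and 9, the side-effect rule can act at any time, and the site investigator reviews adverse events within 24 hours. This stands. It would not find a silent rise, but the documents do not show how likely one is: the prednisone risk list does not mention blood pressure.

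**Sites may measure anyway.** A child seen on site may well be weighed, and the Manual of Operations, which was not available, may require it. This also stands as an uncertainty. The protocol itself sets the rules and the schedule, and it does not require these measurements.

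**The dose claim is conditional.** Nothing fixes the mg amount between weighings, supply at months 1, 3 and 9 rests on one general sentence, and the protocol does not say how drug is supplied when the contact is by phone. This is accepted. The end-of-interval doses are also the lowest points, and the averages are milder.

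**The systolic rule.** A reader might infer that it is unworkable. The documents do not support that, because the natural reading works at months 6 and 12. A reader might also infer that comparison with the previous visit never catches a stepwise rise, so that a fixed baseline is needed. That is not supported either. With a rise of 10 mm Hg per visit, the current 6 v 0 comparison sees +30 and flags about 89–97% of children, and even unconfirmed consecutive comparisons flag about 87–95% over the year. A confirming repeat would lower the latter, which is a fair argument for considering a baseline reference. But a fixed baseline counts normal rise with age: at an assumed 15 mm Hg over the year and SD 8, a baseline rule with an independent confirming repeat triggers in 39% against 34% for the current rule. That choice is a debatable trade-off and does not follow from the gap in the schedule.

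**Conclusion.** The point holds as a gap in scheduled measurement. If the protocol is followed as written, two of five dose-reduction rules have no on-treatment reading for six months and about 52 doses, although safety visits already exist at months 1 and 3. This rests on the protocol text alone.

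The dose point holds only if the mg amount stays at the last recorded weight. Its size depends on growth: average doses of about 9.1, 8.4 and 7.3 mg/kg/week for assumed six-month gains of 20%, 40% and 80%. A reader might infer overdosing or a biased motor result. Growth at a fixed mg amount lowers the dose per kg, and nothing in the documents shows an effect on the Bayley-III outcome.

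The trigger rates depend on the assumed SDs of 8–12 mm Hg. They show why added readings need a confirmation step, and they are not estimates for this trial. Sample size is unaffected. The change should be made because it is cheap and concerns safety. Confidence is medium, since the Manual of Operations may already cover part of it.

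**What to change.** 1. Add blood pressure and weight to the month 1, 3 and 9 columns of Table 1, taken on site, or by local staff when blood is drawn locally.
2. State that the mg dose is recalculated from the current weight at each dispensing visit.
3. In the systolic rule, define the comparator as the last recorded reading, and require a repeat at the same visit that also exceeds the threshold before the dose is reduced.

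**Cost.** A wording and table amendment with no new visit. Families using phone visits need an infant weight and blood pressure, with a repeat if high, taken locally and sent to the site at up to three contacts per child: at most 3 × 25 = 75 contacts. The repeat misses some true rises that a single reading would flag. If its error is strongly shared with the first reading, chance triggers stay near today's level or somewhat above it.

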Statistical plan for
Historically Controlled Trial of Corticosteroids in Young Boys With
Duchenne Muscular Dystrophy

Statistics will be performed with Excel (Microsoft Inc.) and GraphPad Prism (GraphPad Software, La Jolla, CA). P-values will all 2-tailed. A p value of <0.05 will interpreted as showing statistical significance. Mann Whitney U will be used for non-parametric data.

Analysis of data will be performed in two ways. First, the change over one year in the Treated Cohort will be compared to the previously published Historical Control Cohort (HCC). Second, repeated measures (paired t- tests) were used to analyze each boy's performance over his own baseline.
